8.6 Analysis of Primary Efficacy Endpoint

Hypothesis:

The null hypothesis is that there is no treatment group difference (NAL ER vs. placebo) for the primary efficacy endpoint and the alternative hypothesis is that a treatment group difference exists.

Statistical Decision Rules

Unless otherwise indicated, all tests will be 2-sided, and differences resulting in a p-value <0.05 will be considered statistically significant.

The primary efficacy endpoint is the difference between the percent responders at Week 14 for the NAL ER treatment arm versus the placebo arm.

A responder is defined as a subject with a ≥ 4 -point decrease in the 7-day average WI-NRS from baseline to Week 14.

The proportions of responders in NAL ER and placebo will be compared using a logistic regression model, with baseline WI-NRS as a covariate and country as fixed effect, as described below. Missing Week 14 WI-NRS data will be set to missing.

Sample SAS code:

```
proc genmod data=winrsa descending; where avisitn ge 3;
class usubjid avisitn trt posite ;
model resp = trt avisitn avisitn*trt posite base
/ dist=binomial;
repeated subject=usubjid / withinsubject=avisitn
type=un;
lsmeans trt*avisitn /cl ilink diff oddsratio;
Ods output diff=diff lsmeans=lsm ;
run;
```

* Estimate Response rate and SE;

Recoding the resp to a new resp variable

```
data winrsa; set winrsa;
if resp = 0 then respnw = 2;
else if resp= 1 then respnw = 1;
run;
```

Using proc freq to create the binomial dataset;

```
proc sort data = winrsa; by avisitn trt;
proc freq data = winrsa; by avisitn trt;
tables respnw/ out = FreqCount binomial ;
exact binomial;
ods output binomial=bin;
run;
```

The variable *_bin_* is the response rate for resp = 1;
The variable for SE is *E_bin*

* Estimate Odds ratio and CI;

These are provided in the diff dataset and can be output directly.

run;

Sensitivity analysis

To assess the impact of the above “treatment failure” rule, the missing data strategy will employ the control-based multiple imputation (MI) procedure and delta-based multiple imputation (or tipping point analysis) to assess the sensitivity of the study conclusions to the missing response data. Multiple imputation provides a better estimate of the effect of missing data on the variance of the estimates and is therefore less likely to result in false positive inferences. Control based imputation restricts imputing responses for the active arm participants to responses in the control arm. This process will be done sequentially for each time point with missing responses. The process is described by Ratitch & O’Kelly (2011)⁶ and summarized below. These methods will be implemented in SAS9.4® using PROC MI and PROC MIANALYZE and are based on pattern mixture models that assume monotone drop out.

In order to meet the monotone assumption, if there are intermittent missing data points, these will be first imputed using a Monte Carlo Markov Chain Method (MCMC). Please refer to [Appendix](#).

Intermittent missing data is typically a very small percentage of overall missing and is not expected to affect or bias inference. The MI procedure will be used for subjects with missing Week 14 WI-NRS data and/or who withdraw prematurely prior to Week 14.

8.6.1.1 Control Based Imputation.

The monotone missing data is sequentially imputed using the responses of the control group only. This is done sequentially for each time point. In order to ensure that only the control group data is used for active arm subjects with responses missing starting at time t1, the data set is subset to include all control subjects and only those active arm subjects who have missing values at time t. This is repeated for each time point going forward – please refer to [Appendix](#) for details.

PROC MI is then used to impute all missing values for t1 in the treatment arm using the standard PMM imputation approach. Please refer to [Appendix](#) for details.

The data set is combined with the rest of the data and a new subset is created for active arm recipients with responses missing for time t2. This is repeated for each subsequent time point.

Finally, each fully imputed data set is analyzed using the appropriate procedure, e.g., Proc Mixed, and then the results are collated using PROC MIANALYZE.

After imputing the missing values, logistic regression will be performed 50 times using imputed datasets. The estimates will be combined using PROC MIANALYZE procedure.

8.6.1.2. Tipping point analysis.

The tipping point analyses is to assess how much the missing data would have to differ from the imputed data that is based on a MAR assumption in order to reverse the conclusions of the trials. This can be done using PROC MIANALYZE. Tipping point analyses are typically used to ensure that missing data imputation does not create false positive inferences.

this time, we do not know if the current study will result in an inference that suggests treatment benefits. The TPA description below describes the derivation for treatment benefit and absence of treatment benefit. The primary decision to be made in the tipping point analysis is determining the value of delta). In this case, we have used the standard deviation of the efficacy measure of the subjects in the treatment group who completed all visits.

Non-monotonic data will be imputed as above. The Monotonic missing data will be the result of subjects dropping out of the study. For the primary endpoint, we are only concerned with responders (decrease ≥ 4 points in the WINRS scale) and non-responders at week 14. So in this case we will be looking at the dropouts in the stable double-blind phase.

Determining the delta for the tipping point analysis would follow the following steps. Impute missing values one visit at a time as above for control subjects; Please refer to the [Appendix](#) for details.

1. Estimate the mean scores and standard deviations (SD) in those who completed all visits;
2. Use the standard deviation of the completers as the initial delta value for the dropouts;
3. If the week 2 value is missing in the original data, then in the TPA, the imputed value for week 2 will be modified by adding the SD of the completer's week 2 value to the imputed value.

Assuming that the scores in completers indicate better outcomes than dropouts, i.e. mean score in completers $<$ mean score in dropouts, the TPA score will first assume worse outcomes in dropouts. The delta value will therefore be added to the mean score of completers to impute missing scores for the dropouts. Since the data set has been converted to monotonic missing data, if week 2 values are missing, week 4, week 6, week 10 & week 14 will also be missing & have been imputed assuming MAR. Therefore, each of these values will be increased by the SD of the corresponding week for the completers. This will be repeated for each set of missing values, i.e.,

if the week of dropout is week 4, then week 4, week6, week 10 & week 14 imputed values will be modified.

4. After we run the models adding the SD to the imputed values, we will also subtract the delta value to assess how inference might change if dropouts had better outcomes than completers and the delta values will be subtracted from the mean scores of completers to impute values for the dropouts.

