5. SAMPLE SIZE AND POWER

The planned sample size of approximately 240 subjects (120 per group) is based on assumed responder percentages for placebo and NAL ER of 25% and 45%, respectively. These responder percentages represent estimates based on the Week 10 data from the TR03 study. Power is set at 90% with a 2-sided significance level of 0.05.

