5.2 Calculations

Approximately 30 - 45 sites are expected to participate in the current study. In SAS PROC POWER, the LOGISTIC setting was used to approximate the power for a chi-square test comparing the 2 treatment groups with respect to response, without site in the model, and a CMH

test comparing the 2 treatment groups with respect to response, with site in the model. In a model without site, the sample size was n=234 (117 per treatment group). The model with sites included was originally considered with the following assumptions: 30 sites of varying sizes (6 sites with 1% of the total sample each, 6 with 2%, 6 with 3%, 6 with 4%, 3 with 5%, 1 with 6%, 1 with 8% and 1 with 11%); and varying responder rates among sites (one fixed as having the lowest, and the next lowest having an odds ratio of 1.05 compared to the lowest and so on, until the one with the highest, which has an odds ratio of $[1.05]^{29} \approx 4.12$ compared to the lowest; this variation among sites is perhaps larger variation among sites than one would expect). In the PROC POWER runs, this site effect was specified in fixed order, and the site size was randomly scrambled. In 10 runs, the sample size needed for 90% power ranged from 239 to 242, averaging 240.7. Hence, the final target sample size is taken to be 240. With a sample size of 240, the study will have 80% power to detect a difference if the NAL ER 162 mg responder rate is as low as 41.8%.

To address the concern of the reliability of the estimates of treatment effectiveness from the previous studies, an adaptive mid-course sample size re-estimation procedure will be performed when 50% of the subjects have either completed the Week 14 primary endpoint assessment or terminated from the study early. The data for the re-estimation of sample size will be unblinded to an independent statistician and the sample size may be increased up to the predefined maximum allowable sample size if the conditional power is within the promising zone; therefore, this re-estimation will not inflate the type I error.

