In this analyses, the concept is to assess the level of bias introduced by the missing at random assumption in the first simple MI performed above. In this approach, subtract a pre-determined value from the imputed values for the actively treated group. this approach uses the standard deviation of the scores for the completers in the treated group. It could be a %change in the mean or a variety of other values depending on the expected effect. The suggested approach is below.

```

data mi_chk1; set adeff;
where param="WINRS Average" and paramcd="WINRSA" and dtype="" and 2 <=avisitn<=5;
run;
data mi_chk1; set mi_chk1;
if trt01pn = 1 then trt = 1;
else if trt01pn = 2 then trt = 0;
run;

proc sort data = mi_chk1; by trt usubjid;
proc transpose data=mi_chk1 out=mi_chk2 prefix=v;
by trt usubjid;
id avisitn;
var aval;
run;
  by trt ;
  var v2-v5;
run;

```

Next estimate the standard deviation of the WINRS score in the control group and active treatment group by visit among those subjects who completed all visits.

Then merge a data set with the delta value to the data set where values will be imputed.

Use proc univariate to obtain the mean values, stddev, range for the completers in the treated group in order to identify a delta value (SD in this case. Other approaches could use the median, or percentiles).

Suggested code is below.

```

proc sort data = mi_chk1; by usubjid;
data base; set mi_chk1 ( Keep = usubjid base country complfl); by usubjid; if first.usubjid;run;
proc sort data = mi_chk2; by usubjid;
proc sort data = base; by usubjid;
data mi_chk2; merge mi_chk2 base; by usubjid;
run;
proc univariate data = mi_chk2; where complfl = 'Y'; by trt;
var v2 v3 v5 v5;
output out=WINRSCOMP_uni mean=Meanv2 Meanv3 meanv4 meanv5
      std=stdv2 stdv3 stdv4 stdv5
      range=range_v2 range_v3 range_v4 range_v5;
run;

```

```

proc sort data = WINRSCOMP_UNI; by trt;
data mi_chk3; merge mi_chk2 winrscomp_uni; by trt;
run;
  
```

Fill in the intermittent missing data using the following code.

```

proc sort data = mi_chk3; by treatment;
proc mi data=mi_chk3 seed=12345 NIMPUTE=50 out=MI;
  by trt01pn;
  mcmc impute=monotone;
  var Visit2 – Visit5;
run;
  
```

Create an id variable to identify which visits were imputed in the active treatment group.

```

data control_mi; set mi; where trt = 0; run;
data NALER_mi; set mi; where trt = 1;
Data NALER_MI; Set NALER_MI;
if V2 = . then Imp_v2 = 1; else Imp_V2 = 0;
if V3 = . then Imp_v3 = 1; else Imp_v3 = 0;

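### SAP 8.6.1.2 defines the tipping-point shift in two incompatible ways, and Appendix 12.3 does not settle which one applies

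*SAP*

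**What the plan says.** SAP 8.6.1.2 opens by giving the purpose: to find how far the missing data would have to depart from values imputed under MAR before the conclusion reverses. It then describes the shift in two ways.

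- **Shift on the imputed value.** Step 3 says the imputed Week 2 score "will be modified by adding the SD of the completer" group for that visit. The following text, on the later visits of the same dropout, says: "Therefore, each of these values will be increased by the SD of the corresponding week for the completers".
- **Shift on the completers' mean.** Between those two statements stands: "The delta value will therefore be added to the mean score of completers to impute missing scores for the dropouts". Step 4, on the opposite direction, begins with the imputed values and ends: "the delta values will be subtracted from the mean scores of completers to impute values for the dropouts".

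The section takes the size of delta from treatment-group completers, but applies it to dropouts without naming an arm. Appendix 12.3 does name one; its instruction is to "subtract a pre-determined value from the imputed values for the actively treated group". Its code sets the imputation flags for NAL ER only and lists shifts of 0.25, 0.5, 0.75 and 1 SD in each direction. SAP 8.6.1.2 refers to the appendix for details, but the appendix describes itself as guidance and not as the exact code. Nothing says which text governs.

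**The concern.** The two rules are different imputations. Adding c × SD to an imputed value keeps the spread of the imputed scores and returns the MAR analysis at c = 0. Completers' mean plus c × SD replaces all imputed scores in an arm with one number. Whether a dropout is a responder then depends only on baseline, there is no between-imputation variation for dropouts, and c = 0 is not MAR. A tipping value on that scale does not answer the question the section asks.

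At stake is how the robustness of the primary result is reported. Two programmers following the same section could report different tipping points from the same data.

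**Working it through.** **Plan's own figure.** The SAP gives no tipping-point result. Its planning inputs do reproduce. They are "assumed responder percentages for placebo and NAL ER of 25% and 45%, respectively" and "Power is set at 90% with a 2-sided significance level of 0.05". Per arm, n = [1.960·√(2·0.35·0.65) + 1.282·√(0.25·0.75 + 0.45·0.55)]² / 0.20² = (1.322 + 0.845)² / 0.04 ≈ 117.4, so 118 per arm or 236 in total. SAP 5.2 states: "In a model without site, the sample size was n=234 (117 per treatment group)".

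**Inputs for the comparison**

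- 180 per arm (Protocol, 360 randomized 1:1).
- Missing 33% NAL ER and 9% placebo: TR03 non-completion, 6/18 and 2/22 (Protocol 13.1). No TR11 figure is given.
- Assumed: response under MAR 42% vs 23%; Week 14 SD 2.35; baseline mean 8.4, SD 0.9 before clipping to 7–10; slope of Week 14 on baseline 0.6.
- Test: z = (pA − pP) / √[pA(1−pA)/180 + pP(1−pP)/180], tipped when z < 1.96. This uses a single-imputation standard error.

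**Dropout response (simulated, 10⁶ per arm), c = 0, 0.25, 0.5, 0.75, 1**

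- Imputed value + c × SD: NAL ER 42.0, 32.5, 23.9, 16.8, 11.2%; placebo 23.0, 16.1, 10.7, 6.7, 4.0%.
- Completers' mean + c × SD: NAL ER about 30, 11.8, 0, 0, 0%; placebo 0% throughout.

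The zeros follow directly. A 42% response corresponds to a NAL ER mean near 4.87. At c = 0.5 the constant is 4.87 + 1.18 = 6.05, so a 4-point fall needs a baseline of 10.05 on a scale that ends at 10. At c = 0 the mean rule already gives about 30% where MAR gives 42% (NAL ER), and 0% where MAR gives 23% (placebo).

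**z by reading**

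| c | Imputed, NAL ER only | Imputed, both arms | Mean, both arms |
|---|---|---|---|
| 0 | 3.93 | 3.93 | 3.61 |
| 0.25 | 3.30 | 3.44 | 2.39 |
| 0.5 | 2.73 | 2.98 | 1.57 |
| 0.75 | 2.25 | 2.59 | 1.57 |
| 1 | 1.87 | 2.27 | 1.57 |

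Two cells by hand:

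- Imputed, NAL ER only, c = 1: pA = (2/3)(0.42) + (1/3)(0.112) = 0.317; z = (0.317 − 0.230)/0.0468 = 1.87.
- Mean, both arms, c = 0.5: pA = (2/3)(0.42) = 0.280; pP = (20/22)(0.23) = 0.209; z = 0.071/0.0452 = 1.57.

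**Range.** With 20% NAL ER dropout and placebo still 9%, the mean rule in both arms gives at worst pA = 0.8 × 0.42 = 0.336 and z = (0.336 − 0.209)/0.0465 = 2.73. The imputed-value rule, NAL ER only, at c = 1 gives z = 2.70. Nothing tips.

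**With Rubin's rules.** Trials were simulated with 50 imputations and a logistic model (40% vs 27%, 33%/9% missing). Among MAR-significant trials, those that tipped at the first step of 0.25 SD were:

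| SD | Imputed, both arms | Imputed, NAL ER only | Mean, both arms |
|---|---|---|---|
| 2.0 | 20 of 75 | 24 of 75 | 46 of 75 |
| 3.0 | 18 of 81 | 24 of 81 | 68 of 81 |

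At 10% dropout per arm (SD 2.5), most trials never tipped under any of the three: 77, 61 and 76 of 84.

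**Appendix code.**

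- It subtracts first, where 8.6.1.2 adds first.
- It shifts v3–v5 when the v3 flag is set, v4–v5 again under the v4 flag, and v5 again under the v5 flag. A subject missing from v3 carries all three flags, so Week 14 moves by 3c × SD.
- The long-format data set is then built from mi_reg, which holds the unshifted values, and not from mi_reg6.

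**The case against.** The strongest reply is that the mean sentences are loose wording. The stated purpose, step 3, the opening of step 4 and all of the appendix code work on the imputed value, and a constant per arm would make 50 imputations pointless for dropouts. The arm question is mostly silence in 8.6.1.2, which the appendix fills. This is also a sensitivity analysis, so the primary test is untouched. Most of that stands, and it shows which rule to keep. It does not remove two sentences that prescribe a different calculation, and the appendix cannot override them while it calls itself guidance.

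A reader might infer something stronger: that the same data would tip at 0.25 SD under one reading and never under another. The documents do not support that as the expected size. Under the inputs above, the 0.25 SD result (z about 1.9) needs the completers'-mean anchor of 8.6.1.2 combined with the NAL ER-only scope of Appendix 12.3, and no single passage states that pair. At 45% vs 25%, or with SD 2.0, that pair has z about 2.2 at 0.25 SD and has not tipped. Arm choice alone, under the imputed-value rule, produced the 0.25-versus-never split in only 3 of 119, 4 of 59 and 4 of 84 simulated MAR-significant trials, and in none of the 33%/9% scenarios.

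**Conclusion.** The concern holds as a conflict in the anchor of the shift, with an unstated arm and an appendix that differs in sign and code. The mean rule is wrong for the stated purpose and is more than a missing detail. Between readings that the text supports, the tipping point moves from 0.25–0.5 SD to 0.75–1 SD or beyond the grid, given TR03-like dropout and the assumed response, SD and baseline. With 20% NAL ER dropout no reading tips within 1 SD. Never tipping here means only not within the SAP's grid. The documents give no TR11 dropout, SD or effect, so the size in the actual data cannot be known from them.

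**What to change.** In SAP 8.6.1.2, delete the two statements that add delta to, or subtract it from, the completers' mean. State one rule: value = MAR-imputed value + c × completers' SD at that visit. Apply it to imputed NAL ER values only, with placebo left at MAR and positive c meaning worse itch.

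Make Appendix 12.3 match:

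- use the same sign convention;
- shift each imputed visit once only;
- build the long-format data set from the shifted mi_reg6.

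A useful program check is that c = 0 returns the MAR result exactly. The cost is SAP wording and a few lines of code, with no new data. It should be settled before unblinding.

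Deleting the two statements while leaving the appendix code as it stands would not be enough. The text would then describe a single shift, while the code shifts some Week 14 values up to three times and analyses the unshifted set.

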8.6.1.3. Sensitivity Analysis for Subjects who take Prohibited Medications

This analysis is to assess the impact of concomitant medications that might affect the primary endpoint. The medications listed below are considered inter-current events (ICEs) confounding with the efficacy outcomes.

- μ -opioid receptor agonists (e.g., codeine, oxycodone, hydromorphone, oxymorphone, morphine, fentanyl, tramadol, butorphanol, pentazocine, meperidine, methadone)
- Opioid receptor antagonists naltrexone and nalmefene
- Antihistamines (topical or systemic)
- Topical calcineurin inhibitors
- Topical corticosteroids
- Topical capsaicin
- Anti-convulsant class drugs
- Cannabinoid agonists
- Topical doxepin
- Thalidomide or methotrexate
- Cyclosporin A
- Biologics with an immune suppressive effect*
- Investigational drug products*
- Cryosurgery
- UV-therapy

Efficacy data on subjects who experience an ICE will be set to missing at the designated time points after the start of such events. The analysis will provide an answer to the question that is crucial to individual subjects; “If I take this study medication as part of my treatment regimen, without adding any further medications that may impact the underlying disease, what response (response is defined as a ≥ 4 -point reduction in the 7-day average WI-NRS) might be anticipated after 14 weeks?”

Sensitivity analysis using missing data handling approaches will also be performed as outlined in the [Appendix](#).

In addition, the primary endpoint will be analyzed using the PP population.

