23. Potential subjects receiving systemic corticosteroids or local steroid injections of the PN lesions require a 4-week washout. These medications are prohibited for the duration of the study. Please refer to [Table 3](#) and [Section 9.1.3.1](#).
24. Potential subjects are excluded if they have had any addition or discontinuation of their regularly used prescription drugs, or any changes in the doses of their regularly used prescription drugs in the 14 days prior to the screening period e-diary WI-NRS collection.
25. Potential subjects taking central nervous system suppressants, such as barbiturates, benzodiazepines (with the exception of short-acting benzodiazepines specifically used on an intermittent and as needed basis), anxiolytics other than benzodiazepines, neuroleptics, and clonidine are excluded. These medications are prohibited for the duration of the study (see [Section 10.6.2](#), [footnotes 1](#) and [2](#) to [Table 3](#) for definitions of ‘short-acting benzodiazepines’).

Cardiac-related Exclusions:

26. Subjects with a history of congestive heart failure of Class 2 or higher as graded using the New York Heart Association scale (see [Appendix 9](#)).

27. Subjects with a history of angina pectoris Grade 2 or higher as graded using the CanadianCardiovascular Society grading scale (see [Appendix 8](#)).
28. History of ventricular tachycardia, Torsade de Pointes, or family history of sudden death.
29. Myocardial infarction or acute coronary syndrome within the previous 3 months, as reported by the subject.
30. Serum potassium below the laboratory lower limit of normal. Note: If the initial screening value is low, but not considered clinically significant in relation to cardiac risk, then potassiumsupplementation may be prescribed and the serum potassium level repeated once at least 2 weekslater, during the screening period. If the repeat potassium remains < LLN, then the subject mustbe a screen-fail.
31. QTcF interval > 450 ms (mean of 3 screening ECG QTcF values) if QRS < 120 ms (mean of 3 screening ECG QRS values); QTcF interval > 480 ms in the presence of Right Bundle Branch Block (RBBB) and/or QRS \geq 120 ms.
32. Heart rate < 45 bpm on any screening measurement either in the clinic or on the central ECG readings.

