Topical corticosteroids	Excluded within 14 days (e.g. 14-day washout) prior to the start of the screening e-diary WI-NRS collection	Prohibited (except topicals for limited 'Itch Intervention' as in Section 10.6.4)
Systemic corticosteroids	Excluded within 4 weeks (e.g. 4-week washout) prior to the start of the screening e-diary WI-NRS collection.	Prohibited
Topical capsaicin	Excluded within 14 days (e.g. 14-day washout) prior to the start of the screening e-diary WI-NRS collection	Prohibited (except for limited 'Itch Intervention' as in Section 10.6.4)
Anti-convulsant class drugs (e.g., gabapentin or pregabalin)	Excluded within 14 days (e.g. 14-day washout) prior to the start of the screening e-diary WI-NRS collection	Prohibited
Medications with anti-itch activity as documented in published literature even if this effect is not addressed in drug labelling or chronic itch guidelines.	Consult with the Medical Monitor for assessment of washout duration	Prohibited
Cannabinoid agonists	Excluded within 14 days (e.g. 14-day washout) prior to the start of the screening e-diary WI-NRS collection	Prohibited
Topical doxepin	Excluded within 14 days (e.g. 14-day washout) prior to the start of the screening e-diary WI-NRS collection	Prohibited (except for limited 'Itch Intervention' as in Section 10.6.4)
Thalidomide or methotrexate	Excluded within 14 days (e.g. 14-day washout) prior to the start of the screening e-diary WI-NRS collection	Prohibited
Cyclosporin A ³	Excluded within 6-weeks (e.g. 6-week washout) prior to the start of the screening e-diary WI-NRS collection	Prohibited

Table-3. Prohibited Medications and Washout Requirements		
Concomitant Medication	Study Entry (see Section 9.5)	During Study
Non-insulin biologics (including monoclonal antibodies) that modify the immune system ³	Excluded within 3-months (e.g. -month/12-week washout) prior to the start of the screening e-diary WI-NRS collection	Prohibited
Investigational drug products	Excluded within 4 weeks (e.g. 4-week washout) prior to the start of the screening e-diary WI-NRS collection Investigational monoclonal antibodies are excluded within 3months (e.g. 3-month/12-week washout) prior to the start of the screening e-diary WI-NRS collection ³	Prohibited
Cryosurgery	Excluded within 14 days (e.g. 14-day washout) prior to the start of the screening e-diary WI-NRS collection	Prohibited

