6.3. Per-Protocol population (PP)

The per-protocol (PP) population will include all subjects in the mITT population without any major protocol deviations that could have influenced the validity of the data for the primary efficacy variable.

The deviations can include, but are not limited to: e.g. inclusion criteria 1-6 and exclusion criteria 1-3, 16, 17, and 19-25 must have been satisfied.

- Key inclusion/exclusion criteria not satisfied.
- Use of prohibited concomitant medications.
- Inadequate investigational product compliance (<50% compliant), which will be determined before breaking the blind.

The subjects to be excluded from the PP population will be identified in a blinded fashion and documented in a memo prior to the database lock and unblinding.

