9 CHANGES TO PLANNED ANALYSIS FROM STUDY PROTOCOL

The following changes were agreed upon

1. Sites were changed from random effects to region (US or Europe) which is being treated as a fixed effect.
2. LOCF was excluded from imputation methods.
3. The ranked outcome for adjustment for multiplicity was changed. The ItchyQoL measure & the PROMIS scale were excluded from the ranking and replaced with PAS (5a)
4. The analyses for prohibited medication were changed to set all efficacy outcomes to missing from the date of ingestion of the prohibited medication. Previously, missing outcomes were set = non-responders.
5. A new set of simple multiple imputation models were added to assess the impact of missing efficacy measures due to the use of prohibited medications.

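### The SAP's list of intercurrent-event medications names only topical corticosteroids, although the protocol also prohibits systemic and lesion-injected steroids; the list conflicts with the SAP's general rule on prohibited medication

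*SAP*

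**What the plan says.** SAP 8.6.1.3 introduces the analysis with a list of 15 medication or procedure classes: "The medications listed below are considered inter-current events (ICEs) confounding with the efficacy outcomes". The consequence of an event is stated after the list: "Efficacy data on subjects who experience an ICE will be set to missing at the designated time points after the start of such events". The stated aim is to tell a patient what response to expect at 14 weeks if nothing else that may act on the disease is added. The one corticosteroid entry is "Topical corticosteroids". SAP 8.6.3 applies the same analysis to PAS item 5a.

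Protocol 9.5.2, exclusion criterion 23, says of the other routes: "systemic corticosteroids or local steroid injections of the PN lesions require a 4-week washout. These medications are prohibited for the duration of the study". In Protocol Table-3 (section 10.6.2), "Systemic corticosteroids" has its own row, separate from the topical row. It is marked as prohibited during the study, without the limited itch-intervention exception that topical steroids have. Lesion injection has no row of its own in Table-3.

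SAP section 9 item 4 describes the prohibited-medication rule more generally. The change was to "set all efficacy outcomes to missing from the date of ingestion of the prohibited medication". Item 5 says that "simple multiple imputation models were added to assess the impact of missing efficacy measures due to the use of prohibited medications".

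**The concern.** The analysis is only as good as its event list. A subject given an oral steroid course, or an injection into the lesions, has received a treatment that may act on the disease and that the protocol forbids. Under the list, that subject's later itch scores and lesion assessments count as if they reflected study drug alone. A subject using a topical steroid has later data removed. Protocol 7.1 itself counts topical, systemic and intra-lesion steroids among the treatments that have been tried in this disease, so nothing in the plan supports treating the three routes differently here.

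At stake is whether two sensitivity analyses, one on the primary endpoint and one on a protocol key secondary endpoint, answer the question they state. A programmer following the list would keep these data. A programmer following section 9 item 4 might remove them. The plan should not leave that choice open.

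**Working it through.** **1. Steroid routes, side by side**

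| Route | Protocol, during study | SAP 8.6.1.3 list |
|---|---|---|
| Topical | Prohibited, with a limited itch-intervention exception (Table-3; 10.6.4) | Listed |
| Systemic | Prohibited (exclusion 23; Table-3) | Not listed |
| Injection into lesions | Prohibited (exclusion 23) | Not listed |

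Two of the three prohibited routes are absent.

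**2. Could another entry cover them?** No. The list has no open-ended wording at list level. Routes are given entry by entry: antihistamines are listed for both topical and systemic use, whereas steroids are listed as topical only. The entries for methotrexate, cyclosporin A and immune-suppressive biologics show that the list is not confined to topical agents, but none of them is a corticosteroid.

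**3. Does the order suggest intent?** The SAP list follows the order of Table-3. Table-3 runs topical corticosteroids, systemic corticosteroids, topical capsaicin. The SAP goes straight from the first to the third. Neither 8.6.1.3 nor section 9 gives a reason.

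**4. List against general rule.** Section 9 item 4 refers to prohibited medication without naming drugs. If it is operative, it reaches systemic steroids and conflicts with the list. If it is only a summary, the list governs and the omission stands in full. Either way the text needs an edit. The timing also differs: 8.6.1.3 uses designated but undefined time points after the start of the event, and item 4 uses the date of ingestion. Ingestion does not describe an injection, nor the topical, cryosurgery and UV entries already on the list.

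**5. Scale per subject.** The plan gives no figure to reproduce. Inputs are 180 per arm (360 randomized 1:1) and the planning response rates of 45% and 25% (Protocol 13.1), which give 81 and 45 responders. As a simplification, a subject set to missing drops out of the Week 14 rate.

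- One responder wrongly kept, NAL ER: 81/180 = 45.00% against 80/179 = 44.69%, or +0.31 points.
- One responder wrongly kept, placebo: 45/180 = 25.00% against 44/179 = 24.58%, or +0.42 points.
- One non-responder wrongly kept, NAL ER: 81/180 = 45.00% against 81/179 = 45.25%, or -0.25 points.
- One non-responder wrongly kept, placebo: 45/180 = 25.00% against 45/179 = 25.14%, or -0.14 points.

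In general, if a share u of an arm uses these steroids, responding at rate q against p in the rest, the arm's rate shifts by u × (q − p). The documents give neither u nor q, so neither the size nor the sign can be fixed.

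**The case against.** The strongest reply is that the SAP already covers these steroids. The section title speaks of prohibited medications, section 9 item 4 states the rule without a list, and systemic steroids are prohibited in Table-3. This has force. A reader might infer that data after systemic or injected steroids will certainly be kept, and the documents do not support that much. They do show that the only operative list omits these steroids while a general sentence elsewhere may include them.

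A second reply is that the per-protocol analysis is the protocol's own check. The protocol synopsis presents it as the sensitivity analysis for selected medications that might affect the primary endpoint. SAP 6.3 allows exclusion for prohibited concomitant medication with no drug list, and its example of relevant criteria, "inclusion criteria 1-6 and exclusion criteria 1-3, 16, 17, and 19-25 must have been satisfied", includes criterion 23. This also stands, in part. However, the deviations are ones that can be included rather than must be. The per-protocol analysis removes whole subjects rather than data after use, so it answers a different question. It is planned for the primary endpoint and does not reach PAS item 5a.

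A third reply is that the list may be a deliberate selection, since other Table-3 rows are absent too, such as drugs with published anti-itch activity. No such reasoning is given, and listing the topical form of a class while leaving out the systemic form is hard to square with the stated question. The point does show that defining events by reference to the protocol may be the more robust repair.

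**Conclusion.** The point holds as a conflict between an incomplete list and a general rule. Read literally, the list keeps efficacy data recorded after systemic or lesion-injected steroids in the prohibited-medication analysis of the primary endpoint and in its PAS item 5a counterpart. The primary test is unchanged, and the per-protocol analysis gives partial cover for the primary endpoint. The net effect is unknown. The per-subject figures rest on the planning rates and a complete-case simplification, and they show only that the shift can go either way.

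Two stronger readings should be resisted. First, a reader might infer that for PAS item 5a the error could only raise an arm's rate, because SAP 7.3.4 and 8.6.3 count a missing Week 14 value as non-response. Section 9 items 4 and 5 put that in doubt here: they describe a move away from non-response, with imputation added for prohibited-medication use. Second, a reader might infer that the gap carries into the imputation models of item 5. That item refers to prohibited medications in general and does not invoke the 8.6.1.3 list.

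**What to change.** Before unblinding:

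1. Add systemic corticosteroids and steroid injections of prurigo lesions to the SAP 8.6.1.3 list. Alternatively, define the events by reference to protocol exclusion criterion 23 and Table-3. Table-3 alone is not enough, because it has no row for lesion injection, and the SAP should say which rows count, since some are there for cardiac or respiratory safety.
2. Use one date rule in SAP 8.6.1.3 and section 9 item 4: efficacy data are set to missing from the start date of use, by any route.
3. State that section 9 item 4 refers to the 8.6.1.3 definition.

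The cost is two list entries (or one cross-reference), one aligned sentence on dates, and a blinded check of coded medications. No clinical rule changes. The documents do not say whether unblinding has taken place. If it has, make the same change and report it as an SAP deviation in the clinical study report, as the SAP introduction requires for any departure.
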